Exclusion criteria: Individuals who meet any of the following criteria will not be allowed to participate in this study:

- Individual is sensitive to the components of the study product(s).
- Individual is considered inappropriate by the Principal Investigator (PI).
- Individual has self-reported current skin condition(s) or issues around the sacral or perineal areas, such as open sores, sacral pressure injuries, rash, burns, surgical wounds and/or compromise of skin integrity.
- Individuals who cannot complete all phases of the study requirements.
- Individual requires use of an absorbent undergarment or catheter as the primary incontinence management strategy
- Individuals who are pregnant

Description of Sites/Facilities Enrolling

Rochester Clinical Research located in Rochester, NY

Participants:

Fifty-Six Participants

Description of Study design:

Each participant will be provided with the FitRight® System for the duration of the study. The study products will be used to collect real-life measurement data in order to assess the FitRight® System. Each participant will be asked to wear at least three briefs so that they are wearing each brief during the simulated voids performed by the site staff.

The site staff will perform the simulated void by addition of (90-360 mL normal saline to the brief. The FitRight® System will be assessed for alerts while participants are in the

following positions: supine, sitting, and laying on either left or right side. Each participant will be randomized to either the left or right side. Twenty-two of the fifty-six participants will perform rewet testing procedures. The study results will be used to assess the reliability of the device's absorption to trigger an alert.

Participant Duration: Approximate time will be two hours for each participant to complete the procedures.

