6.4.2 Normal Saline Pours

Once the FitRight® System and tubing is properly setup on the participant, the study staff will pour 90 milliliters (mL) of normal saline (first pour) through the funnel system to enter the brief. Study staff will immediately start a calibrated timer for five minutes once the saline drains from the funnel system. After the five minutes, study staff will document whether the brief did or did not trigger an alert. If the brief triggers an alert, the brief passes and the participant is ready for the next brief. If the brief does not trigger an alert, study staff will pour an additional 150mL normal saline (second pour) through the funnel system and will immediately start a calibrated timer for five minutes once the saline drains from the funnel system.

After the five minutes, study staff will document whether the brief did or did not trigger an alert. If the brief triggers an alert, the brief passes and the participant is ready for the next brief. If the brief does not trigger an alert, study staff will pour an additional 120mL normal saline (third pour) through the filtration system and will immediately start a calibrated timer for five minutes once the saline drains from the funnel system.

After the five minutes, study staff will document whether the brief did or did not trigger an alert. If the brief triggers an alert, the brief passes and the participant is ready for the next brief. If the brief does not trigger an alert, the brief fails, and study staff will pour an additional 120mL normal saline (fourth pour) through the funnel system and will immediately start a calibrated timer for five minutes once the saline drains from the funnel system. After the five minutes, study staff will document whether the brief did or did not trigger an alert. No matter if the brief did or did not trigger an alert, the participant will move onto the next brief. The fourth pour, if required, will help to determine if more volume was needed to trigger the alert or if the system was defective.

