8.2 Randomization

Patients were randomized into two equal groups of 28 by means of a SAS® software generated random seed number and randomization program (Copyright © 2013 SAS Institute Inc.) only for the side position. Twenty-eight patients will complete the test using their right side and 28 will complete the test using their left side. Practically, it will be impossible to blind the staff and patients to the left or right side, as it will be apparent. Thus, the randomization will only be blinded to the analyst to ensure an un bias analysis.

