8.5 Endpoints

8.5.1. Primary Endpoint

FitRight® System alert value of pass (=1) or fail (=0), for each given value of fluid added (90, 150, 120, and 120 mL) and for each rotational position in the brief (sitting, laying supine, left side, and right side)

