8.5.3 Additional Endpoints

The percentage of pass alerts that were correctly triggered ((# passed/tests) x 100) and the percentage of failed alerts ((# fail/ # tests) x 100) will also be evaluated for the whole sample and stratified by volume of fluid and rotational position.

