8.6 Demographics, Variables and Covariates

Age will be collected as a continuous measure, with all participants being ≥ 18 years of age. Age strata will be defined as stratum 1: 18-25 years old, stratum 2: 26-41 years old, stratum 3:

42-57 years old, stratum 4: 58-67 years old, stratum 5: 68-76 years old, stratum 6: 77-94 years old, 95+ years old. Age will be considered for secondary analysis.

Sex will be collected as a categorical equal to 0=male, 1=female, 2=other, or 3=decline to answer. Sex will be considered for secondary analysis.

Brief size will be recorded as a categorical measure and will be used as a proxy for participant weight for secondary analysis.

Rotational position of the participant during the procedure will be collected as a categorical measure equal to 1=sitting, 2=supine, 3=left side or 4=right side. Rotational position will be used in the primary analysis.

Volume of simulated urine added to the brief will be collected as a categorical measure of 90 mL, 150 mL, 120 mL, and 120 mL. The volume of fluid will be used in the primary analysis.

Nominal measures of data collected will include the participant ID, date of first brief application through removal.

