8.9.1 Analysis of Primary Endpoints

The primary goal of this research study is to assess the reliability of the FitRight® Alert Indicator for the full sample and stratified by the four rotational positions, the three different fluid amounts,

and the combination of rotational positions and fluid amounts. Cronbach's coefficient alpha estimate's reliability by determining the internal consistency of a test or the average correlation of items within a test. The pass/fail values from this set of test runs will be compared to the derived variable of whether or not the test should have triggered an alert. Since the variables of interest are dichotomous (pass/fail), the coefficient alpha is equivalent to the Kuder-Richardson 20 (KR-20) reliability measure. It produces a correlation measure between 0 where a high KR20 coefficient (e.g., >0.90) is indicative of a homogeneous test. A reliability of 0.70 or higher for an acceptable rating and 0.80 or higher for a good rating.

In addition, a chi-square analysis will be conducted to determine if any association between rotational position and test status (pass/fail) exists. This analysis will be repeated to examine any possible associations between fluid added and test status (pass/fail).

Spearman correlation analysis will be used to examine possible associations between the key variables of triggered alert value (pass/fail), rotational position (sitting, supine, left side, right side), and fluid volume of 90 mL, 150 mL, 120 mL, and 120 mL with covariates of age, sex, and brief size. Additional t-tests or non-parametric tests will be employed to further examine any significant associations found in the correlational analyses between key and covariate measures.

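### The one pre-specified covariate analysis, a Spearman correlation, is ill-suited as worded: position is nominal, volume is listed as pour increments, and no unit of analysis is set for repeated records.

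*Combined protocol and SAP*

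**What the plan says.** Section 8.9.1 correlates three key variables (alert result, rotational position "and fluid volume of 90 mL, 150 mL, 120 mL, and 120 mL with covariates of age, sex, and brief size"), using Spearman's coefficient. That makes 3 x 3 = 9 correlations. Further testing depends on the outcome: "Additional t-tests or non-parametric tests will be employed to further examine any significant associations found in the correlational analyses". Which test and which rows would be used is not stated.

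Section 8.6 codes position 1 to 4 (sitting, supine, left, right) and sex 0 to 3 (male, female, other, declined). It says volume "will be collected as a categorical measure of 90 mL, 150 mL, 120 mL, and 120 mL". It reserves age, sex and brief size for secondary analysis but names no other method for them. The pass and fail percentages in Section 8.5.3 "will also be evaluated for the whole sample and stratified by volume of fluid and rotational position", so they are not broken down by any participant covariate. Nor do the chi-square tests in Section 8.9.1 include one.

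On the data structure, the synopsis says: "Each participant will be asked to wear at least three briefs". All participants are tested sitting, supine and on one randomised side. Section 8.2 adds: "Twenty-eight patients will complete the test using their right side and 28 will complete the test using their left side". Section 8.5.1 defines pass or fail "for each given value of fluid added (90, 150, 120, and 120 mL) and for each rotational position in the brief". Pours accumulate: in Section 6.4.2, if the first pour gives no alert, "study staff will pour an additional 150mL normal saline (second pour) through the funnel system".

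**The concern.** Whether alerting varies with age, sex or brief size (the plan's proxy for weight) bears on how the device performs across users, and this Spearman step is the gate to every conclusion about it. Four features of the wording cause difficulty.

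1. Position has no natural order, and every participant passes through nearly the same set of positions. Its correlation with a participant characteristic has no clear meaning.
2. The listed volumes are pour sizes, not the amount the brief holds, so their rank order is not the order of wetness.
3. Alert is recorded repeatedly within a participant, while age, sex and brief size are fixed for that participant. Without a stated unit of analysis, the error rate of the test is undefined.
4. Two of the four sex codes have no place in an ordering.

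Two analysts could choose different rows and codings, and reach different covariate conclusions from the same data.

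**Working it through.** The plan gives no figure for this analysis, so there is none to reproduce. Inputs from the documents: 56 participants, 28 left and 28 right (8.2); three briefs each, so 56 x 3 = 168 briefs; up to four pours per brief (5.4); pours of 90, 150, 120 and 120 mL (8.6); significance at P<0.05 (8.9); pass proportions of 0.85, 0.90 and 0.95 (8.1). The documents give neither the within-participant intraclass correlation (ICC) nor the pattern of first alerts. Both are assumed below.

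**Position, one row per brief, complete data.**
- Mean ranks over 168 rows: sitting 28.5 (56 rows), supine 84.5 (56), left 126.5 (28), right 154.5 (28).
- Total sum of squares of the ranks = 362,208.
- Participants differ only in side. Their mean ranks differ by (154.5 - 126.5)/3 = 28/3, so each lies 14/3 from the overall mean.
- Between-participant sum of squares = 168 x (14/3)² = 3,658.7.
- Maximum |rho| for any participant-level covariate = sqrt(3,658.7/362,208) = 0.1005, p = 0.195.
- The maximum is reached if all men lie on one side and all women on the other. Age fully sorted by side gives 0.087, p = 0.26.

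**Position, one row per pour.** The bound no longer holds. Suppose side is balanced by sex and every brief alerts at the first pour, except that one sex needs two pours in the side position. That gives 196 rows, rho = 0.148, p = 0.039. If that sex needs three pours, rho = 0.23, p = 0.0005. The coefficient then reflects how many rows each brief contributed, weighted by arbitrary codes.

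**Volume.** Cumulative volume is 90, 90+150 = 240, 240+120 = 360 and 360+120 = 480 mL. In numeric order the listed values rank 1, 4, 2.5, 2.5; cumulative volume ranks 1, 2, 3, 4. Pouring stops at an alert, so the effect on study data depends on when briefs alert. Two assumed patterns (shares alerting at pour 1/2/3/4/none) give these rank correlations between listed and cumulative volume:

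| Assumed pattern | One row per pour | Last pour of each brief |
|---|---|---|
| 0.59/0.24/0.07/0.05/0.05 | 0.87 | 0.87 |
| 0.32/0.36/0.22/0.05/0.05 | 0.76 | 0.47 |

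**Unit of analysis.** Simulation with 56 x 3 briefs, beta-binomial passes at 85-95%, no true covariate effect and 4,000 runs per setting:

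| Assumed ICC | Pooled brief rows, per covariate | Pooled brief rows, at least one of three |
|---|---|---|
| 0 | about 5% | 13-15% |
| 0.2 | 9-11% | 24-27% |
| 0.4 | 13-15% | 34-38% |

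One pass count per participant gives 4-6% per covariate and 13-15% for at least one of three, at every ICC. That remainder is ordinary multiplicity: 1 - 0.95³ = 14%.

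With one row per pour (2,500 runs), the per-covariate rate at ICC 0, 0.2 and 0.4 is 7-8%, 10-11% and 14-16% under the first alert pattern, but 1%, 3% and 5-6% under the second.

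**The case against.** The strongest reply is that this is a secondary screen whose faults are mostly gaps in wording, and that several tempting readings go too far. Much of that stands.

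- A reader might infer that three of the nine correlations (position with each covariate) can never reach significance. That holds only with one row per brief. Section 8.5.1 suggests one row per pour, where the examples above reach p = 0.039 and p = 0.0005. What remains is that the result is not interpretable under either layout.
- A reader might correlate the four listed volumes with the four cumulative volumes, obtain 0.32, and take that as the loss of information. It counts each pour once, whereas real data are dominated by early pours. Section 8.6 also calls volume categorical with two separate 120 mL levels, which only pour order can tell apart. Coding by pour number is therefore a natural reading and would remove the problem, but the plan does not say so.
- A reader might infer that false positives are inflated. The documents give no ICC, each position uses a new brief and tubing, and the pour-level error can fall below 5%. The supported statement is that the error rate is undetermined.
- The sex codes cause trouble only if other or declined is recorded. With male and female alone, Spearman is a valid two-group rank comparison.
- Section 8.6 already calls the covariates secondary, so an exploratory label is partly there. Alert against age or brief size is a sound rank correlation if analysed per participant.

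**Conclusion.** The concern holds as a minor issue in a supporting analysis. The position-by-covariate correlations should not be run: they are bounded at 0.10 and reflect only left/right imbalance with one row per brief, or are confounded with pour counts with one row per pour. The 0.10 bound assumes complete data and the 28/28 split, but no ICC or pass rate. The volume result depends on an unstated coding, with agreement of 0.47 to 0.87 under the assumed alert patterns. The alert result depends on an unstated choice of rows. With pooled briefs the false-positive rate per covariate runs from about 5% to 15% over assumed ICCs of 0 to 0.4, against 4-6% with one value per participant.

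It would be wrong to read this as a fault in the main results. The pass percentages, the chi-square tests and the sample size of 56 are not affected by this point.

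**What to change.** Amend Section 8.9.1 as follows.

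- Drop the position-by-covariate correlations.
- Analyse alert against age (continuous) and brief size by Spearman on each participant's number of passes out of three, among participants with all three briefs. Section 8.3 admits participants after one full round, so add the proportion of briefs passed as a sensitivity analysis that covers those with fewer than three.
- Compare the pass count between male and female by the Wilcoxon rank-sum test. Set declined to missing and describe other without testing.
- Rank volume as cumulative volume at first alert (90, 240, 360, 480 mL, no alert highest), with one brief per participant within each position. Report these associations as estimates with 95% confidence intervals, not as tests.
- Label all covariate results exploratory and unadjusted for multiplicity.

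The cost is a few lines of SAP wording and no new data. The pass count loses position detail. Estimates stay imprecise: at pass rates of 85% to 95%, 168 briefs give about 168 x 0.15 = 25 down to 168 x 0.05 = 8 failures. Volume within three positions against three covariates gives nine associations. Testing them alongside the three pass-count analyses would make 12 tests, with a simulated 42-45% chance of at least one false positive, which is why they are reported as estimates only. The ordinary multiplicity of about 14% over the three pass-count tests remains.

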8.9.2 Analysis of Secondary Endpoints

The secondary goal is to determine the FitRight® Brief's residual volume capacity . In a subset of 22 participants, evaluate the FitRight® Brief after the brief has absorbed the maximum amount of liquid normal saline via a simulated urinary void (360 mL) in the sitting position. The wetted filter paper will -then be weighed. The rewet measurement will be calculated using the calculation shown below.

Rewet measurement = (weight of the wetted filter paper) - (weight of the dry filter paper)

9. Regulatory and Ethical Considerations

9.1. Confidentiality and Privacy

In all research involving human participants, confidentiality of identifiable information is presumed and must be maintained unless the investigator obtains the express permission of the participant to do otherwise. Participants have the rights to be protected against injury or illegal invasions of their privacy and to preservation of their personal dignity. The more sensitive the research material, the greater the care that must be exercised in obtaining, handling, and storing data.

In order to minimize the risk for loss of confidentiality, investigators should only collect personal information that is absolutely essential to the research activity. If personal data must be collected, it should be coded as early in the activity as possible and securely stored so that only the investigator and authorized staff may access it. Identities of individual participants must never be released without the express consent of the participant. In addition, if an investigator wishes to use data for a purpose other than the one for which it was originally collected and the data are still identifiable (e.g., a code list for the data still exists), the investigator may need to obtain consent from the participants for the new use of the data.

Participant confidentiality and privacy is strictly held in trust by the PI, the staff, and the sponsor. Therefore, documentation, data, and all other information generated will be held in strict confidence. No information concerning the study, or the data will be released to any unauthorized third party without prior written approval of the sponsor. All study data and study records will be managed and stored in accordance with the site's policies on data storage and security. All electronic transmission of data will adhere to Health Insurance Portability and Accountability Act (HIPAA) and any local regulations.

The study monitor, other authorized representatives of the sponsor, representatives of the IRB, and regulatory agencies may inspect all documents and records required to be maintained by the PI, including but not limited to, medical records (office, clinic, or hospital) and pharmacy records for the participants in this study. The clinical study site will permit access to such records.

A master list linking participant numbers to patient name and medical record number will be maintained in a secure database by the PI or paper files in secure cabinet(s). The study participant's contact information will be securely stored at each clinical site for internal use during the study. The PI will agree to notify the sponsor of any intent to move or destroy these documents.

9.2 Safety Oversight

Safety oversight will consist of monitoring of visit activity ADEs and SADEs by the PI, who is suitably qualified and experienced to evaluate any ADEs or SADEs. The PI will review all ADEs and SADEs and make any necessary safety determinations or visit activity modification that are in the best interest of the participant as necessary. See also Section 7.0 ADEs for reporting and management requirements.

9.3 Study Discontinuation

This study may be temporarily suspended or prematurely terminated if there is sufficient reasonable cause. Written notification, documenting the reason for study suspension or termination, will be provided by the suspending or terminating party to the PI, sponsor, and IRB. If the study is prematurely terminated or suspended, the PI, in collaboration with the sponsor, will promptly inform the IRB and will provide the reason(s) for the termination or suspension.

Circumstance(s) that may warrant termination or suspension include, but are not limited to; determination of unexpected, significant, or unacceptable risk to participants as determined by ADE review, insufficient compliance to protocol requirements, and/or data that are not sufficiently complete and/or evaluable.

The study may resume once concerns about safety, protocol compliance, and data quality are addressed, and the sponsor and/or IRB satisfied.

9.4 Study Closeout

Upon completion of the study, Medline Industries, LP. and/or its designees will notify the site of closeout related procedures and will coordinate with the site the return of equipment and/or any unused product. Medline CRA will communicate closely with the PI at that time point and will review all close out steps and materials. All study data, related study documents, and unused study product, will be returned to the sponsor or as per agreement with the study contract. The site will also notify the IRB that the study has been completed.

9.5 Data Handling and Record Keeping

Data collection is the responsibility of the study staff at the site under the supervision of the PI. The PI is responsible for ensuring the accuracy, completeness, legibility, and timeliness of the data reported in the CRFs or any other study activity documentation as part of this study. All the documents should be completed in accordance with Good Documentation Practices (GDP) to ensure accurate interpretation of data.

Final storage of Medline data will be per ICH/GCP guidelines and kept stored in a protected access area for the length of the time required.

9.6 Conflict of Interest Policy

The independence of this study from any actual or perceived influence is critical. Therefore, any actual conflict of interest of persons who have a role in the design, conduct, analysis, publication, or any aspect of this trial will be disclosed and managed.

9.7 Protocol Deviations

It is the responsibility of the PI and study staff to use continuous vigilance to identify and report deviations on a routine basis. All deviations must be reported to Medline Industries, LP. Protocol deviations must be sent to the reviewing IRB per reporting requirements and should be reported to the sponsor in a timely manner. The PI is responsible for knowing and adhering to the IRB requirements.

